2. SYNOPSIS

Name of Sponsor/Company: Revolo Biotherapeutics				
Name of Investigational Product: IRL201104				
Name of Active Ingredient: IRL201104				
Protocol Number: RVLO 121-04	Phase: 2a	Country: United States		
Title of Study: A Phase 2a, Double-blind, Placebo-Controlled, Multi-Center Study to Assess the Efficacy, Safety, and Tolerability of IRL201104 in Adult Participants with Active Eosinophilic Esophagitis (EoE)				
Study centers: Approximately 15 centers in the United States				
Studied period (years): Estimated date first participant enrolled: Sep 2021 Estimated date last participant completed: Jun 2022	Phase of development: 2a			
Study Objectives				
Primary Objective:				

To assess the efficacy of repeat intravenous (IV) doses of 4 mg and 8 mg IRL201104 compared to placebo in adult participants with EoE after 3 doses administered over 14 days as assessed by the change in peak esophageal intraepithelial eosinophilic count per high power field (eos/hpf) at Week 4.				
Secondary Objectives:				

To explore the relationship between IRL201104 treatment and change in symptoms of dysphagia in adult participants with EoE, using the patient-reported outcomes (PRO) instrument Dysphagia Symptom Questionnaire (DSQ).To assess the efficacy of repeat IV doses of IRL201104 in adult participants with EoE after 3 doses administered over 14 days as assessed by thresholds of histologic response at Week 4.To evaluate the safety, tolerability, and immunogenicity of IRL201104 in adult participants with EoE.				
Exploratory Objectives:				

To explore the relationship between IRL201104 and change in clinical outcomes assessments, to include the PROs Patient Global Impression of Severity (PGI-S) and Patient Global Impression of Change (PGI-C), and the clinician-reported outcomes EoE-Endoscopic Reference Score (EREFS) and EoE Histology Scoring System (EoEHSS).To explore the relationship between IRL201104 and the relative change in RNA gene expression to include EoE diagnostic panel (EDP) transcriptome signature.To explore the relationship between IRL201104 treatment on immune cells and markers of inflammation.				

Methodology:

This is a Phase 2a, double-blind, placebo-controlled, multi-center study to assess the efficacy and safety of a repeat-dose regimen of IRL201104 in participants with active EoE. A study diagram is provided in [Figure 1](#).

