8.3.2. Individual Stopping Criteria

Participants will be permanently discontinued from study treatment in the event of:

- Anaphylactic reaction to study treatment
- Treatment with any prohibited concomitant medication or procedure (Section 9.2.2)
- Diagnosis of a malignancy during study, excluding carcinoma in situ of the cervix or squamous or basal cell carcinoma of the skin
- Evidence of pregnancy
- Any infection that:
 - Requires parenteral treatment with antibiotic, antifungal, antiviral, anti-parasitic, or anti-protozoal agent
 - Requires oral treatment with such agents for longer than 2 weeks
 - Is opportunistic, such as tuberculosis and other infections whose nature or course may suggest an immunocompromised status
- Severe laboratory abnormalities, such as:
 - Neutrophil count $<0.5 \times 10^3/\mu\text{L}$
 - Platelet count $<50 \times 10^3/\mu\text{L}$
 - ALT and/or AST values $>3 \times \text{ULN}$ with total bilirubin $>2 \times \text{ULN}$, excluding confirmed Gilbert's Syndrome
- Confirmed AST and/or ALT $>5 \times \text{ULN}$ (for more than 2 weeks)
- Other reasons that may lead to the permanent discontinuation of study treatment include:

- Certain AEs deemed related to the study treatment (eg, severe and prolonged injection site reactions) or study procedures

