12.5. Laboratory Assessments

Detailed instructions for blood sample collection are in the study manuals provided to study centers.

Local Laboratory Assessments:

The following clinical laboratory parameters will be assessed:

Blood Chemistry

Sodium	Total protein, serum	Total and indirect bilirubin
Potassium	Creatinine	Total cholesterol
Chloride	Blood urea nitrogen	Low-density lipoprotein
Carbon dioxide	AST	High-density lipoprotein
Calcium	ALT	Triglycerides
Glucose	Alkaline phosphatase	Uric acid
Albumin	Lactate dehydrogenase	CPK

Hematology

Hemoglobin	Differential:
Hematocrit	Neutrophils
Red blood cells	Lymphocytes
White blood cells	Monocytes
Red cell indices	Basophils
Platelet count	Eosinophils

Urinalysis

Microscopic analysis will only be done in the event of abnormal dipstick results.

Color	Glucose	Red blood cells
Clarity	Blood	Hyaline and other casts

pH	Bilirubin	Bacteria
Specific gravity	Leukocyte esterase	Epithelial cells
Ketones	Nitrite	Crystals
Protein	White blood cells	Yeast

Serological markers

HIV-1/2 antibodies	HBsAg	Hepatitis C virus antibodies
--------------------	-------	------------------------------

Other laboratory tests:

- Serum pregnancy tests will be performed for females of reproductive potential at screening, after which urine pregnancy tests will be performed.
- FSH testing will be performed at screening to confirm post-menopausal status in female participants who have had at least 12 months without menses.
- Coagulation testing (prothrombin time and partial thromboplastin time) will be performed as indicated in the Schedule of Events ([Table 3](#)). Samples for coagulation tests should be obtained before the procedures of endoscopy with esophageal biopsies are performed.

Abnormal laboratory values and laboratory AEs:

- All laboratory values must be reviewed by the investigator or authorized designee.
- Significantly abnormal tests must be repeated to confirm the nature and degree of the abnormality. When necessary, appropriate ancillary investigations should be initiated. If the abnormality fails to resolve or cannot be explained by events or conditions unrelated to the study treatment or its administration, the medical monitor must be consulted.
- The clinical significance of an abnormal test value, within the context of the disease under study, must be determined by the investigator.

Criteria for reporting laboratory values as an AE are provided in Section [12.6.1.4](#).

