15.3.3. Safety Analysis

All on-treatment safety data will be assessed descriptively for AEs, SAEs, clinical laboratory measurements, viral serology, vital signs, physical examinations, and ECGs. No formal statistical analysis will be performed on safety outcomes; inferences, if any, will be derived through clinical review and interpretation.

All TEAEs will be summarized overall and for each body system and preferred term by treatment group, relationship to investigational product, and severity. For tabulations by severity, only a participant's most severe event within the category (eg, overall, body system, or preferred term) will be counted. Adverse events will be dichotomized into "related" (definitely, probably, and possibly) and "unrelated" (unlikely and not related). "Treatment-emergent" will be defined as starting or worsening after the first dose of investigational product. If the start date is missing, the event is assumed to be treatment emergent. All SAEs will be tabulated.

Vital signs, including blood pressure, heart rate, body temperature, respiration rate, and weight will be summarized by treatment group at baseline and at each scheduled visit.

Clinical safety laboratory data will be summarized descriptively by treatment group at baseline and at subsequent scheduled visits. Summaries of safety laboratory parameters will include the first measurement of each scheduled assessment but repeat assessments done at the same study time point will not be included in summary calculations. Laboratory data will also be listed by treatment, participant, and visit. Listings will include scheduled, unscheduled, and repeat evaluations. A listing of markedly abnormal values, as defined in the SAP, will additionally be generated.

Abnormal physical examination findings that suggest a clinically significant worsening from baseline will be reported as AEs and analyzed as such. Clinically significant findings noted prior to start of investigational product treatment will be recorded as medical history and analyzed as such.

Concomitant medications will be tabulated by preferred term, and treatment group. For the purposes of data collection, a medication's usage will be considered concomitant if it was started within 14 days prior to informed consent and continued after administration of the investigational product. If the start date is missing, it will be assumed that the medication was used concomitantly.

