FSH: Follicle stimulating hormone testing will be performed at screening to confirm post-menopausal status in female participants who have had at least 12 months without menses. Collecting at screening visit only.

All observed and change from baseline results of hematology, biochemistry, and coagulation parameters data will be summarized by treatment group, at each scheduled visit using descriptive statistics (n, mean, SD, median, minimum, and maximum) for each scheduled study assessment for the Safety Analysis Set.

For urinalysis data, the continuous variables will be summarized by treatment group at each scheduled visit using descriptive statistics (n, mean, SD, median, minimum, and maximum).

Individual participant data listings of laboratory results will be presented. Values outside of the laboratory's reference range (i.e., those with low or high values) will be flagged in the listings.

The other laboratory tests: FSH, serology and serum pregnancy test will be listed.

12-Lead ECG

The 12-lead ECG will include the following measurements: Ventricular Rate, PR Interval, RR Interval, QRS Duration, QT Interval, QTcF Interval. And it will be summarized for the Safety Analysis Set.

Overall evaluation of safety ECGs will be summarized by treatment group, using frequency counts and percentage of participants as normal or abnormal, and the relevance of the abnormality will be summarized by clinically significant (CS) or not clinically significant (NCS).

Observed and change from baseline in ECG parameters will be summarized by treatment over each scheduled time-point/visit in terms of absolute values using descriptive statistics (n, mean, SD, median, minimum, and maximum).

Individual data listings of ECG results along with the Investigator-identified ECG abnormalities will be presented for each participant by treatment group.

Vital Signs

Vital signs (systolic and diastolic blood pressure, heart rate, respiratory rate, and temperature) will be summarized using the descriptive statistics for each vital sign measurement and change from baseline by treatment group, visit and timepoint using the Safety Analysis Set.

Vital Sign data will be listed by individual time course for each parameter.

Physical Examination

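### The SAP omits the definition and listing of markedly abnormal laboratory values that the protocol assigns to it, and plans no count of participants who meet the protocol's own laboratory limits

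*SAP*

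**What the plan says.** - **Protocol 15.3.3** delegates the definition: "A listing of markedly abnormal values, as defined in the SAP, will additionally be generated". It also says that the summaries use the first measurement of each scheduled assessment and that "repeat assessments done at the same study time point will not be included in summary calculations". Listings include scheduled, unscheduled and repeat evaluations.
- **SAP 7.8** plans the following: "All observed and change from baseline results of hematology, biochemistry, and coagulation parameters data will be summarized by treatment group". For every planned visit it reports the count, mean, SD, median and the two extremes. Values outside the laboratory's "reference range (i.e., those with low or high values) will be flagged in the listings". It gives no threshold, count, shift table, joint ALT/AST and bilirubin display, or conversion to multiples of the upper limit of normal (ULN).
- **SAP Section 11** names two dropped analyses, the EDP transcriptome and the immune markers. The laboratory listing is not among them.
- **Protocol 8.3.2** introduces its treatment-stopping limits with "Severe laboratory abnormalities, such as". **Protocol 8.3.3** gives limits at which a dose may be delayed.
- **Protocol 12.5** places hematology and chemistry under "Local Laboratory Assessments". The synopsis plans "Approximately 15 centers in the United States".

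**The concern.** Safety is a secondary objective, and both documents leave all safety inference to clinical reading of descriptive output. That output should therefore show directly how many participants in each arm reached a laboratory level that the protocol itself treats as important. The protocol left the defining step to the SAP, and the SAP does not take it. What remains is summary statistics of unconverted values from many local laboratories, plus a flag that separates in range from out of range but does not grade the departure. In arms of about 12, a single liver-enzyme or CPK case matters, and no planned table would name or count it as one.

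**Working it through.** The documents give no figure to reproduce on this point. The check sets the protocol's limits against the planned output. Figures marked assumed are illustrations.

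**1. Limits against the planned summaries**

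| Protocol limit | Section | What SAP 7.8 shows |
|---|---|---|
| Neutrophils below 0.5, or 0.5 to 1.0 (10³/µL) | 8.3.2, 8.3.3 | A scheduled minimum shows that a case exists, not how many participants |
| Platelets below 50, or 50 to 100 (10³/µL) | 8.3.2, 8.3.3 | Same |
| ALT/AST above 3×ULN with total bilirubin above 2×ULN | 8.3.2 | Not shown: ULN-based, and separate rows cannot show that both occurred in one person |
| Confirmed ALT/AST above 5×ULN for more than 2 weeks | 8.3.2 | Not shown: ULN-based, and visit-by-visit rows cannot show duration |
| CPK above 10 ULN | 8.3.3 | Not shown: ULN-based |

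**2. Mean and median.** Arm size is 36/3 = 12. Assume 11 participants with ALT at 0.4 to 0.7×ULN and one at a raised value. Mean = (11 × typical + raised)/12.
- Raised value 5.1×ULN: (4.4 + 5.1)/12 = 0.79 to (7.7 + 5.1)/12 = 1.07×ULN.
- Raised value 3.1×ULN: (4.4 + 3.1)/12 = 0.63 to (7.7 + 3.1)/12 = 0.90×ULN.
- The median stays at 0.4 to 0.7×ULN. Neither statistic reveals the case.

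**3. Maximum.** It does show the value, but in raw units. With assumed local ULNs of 35 to 55 U/L, 3×ULN runs from 105 to 165 U/L. A maximum of 120 U/L is 120/35 = 3.4×ULN at one laboratory and 120/55 = 2.2×ULN at another.

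**4. Adverse-event route.**
- Protocol 12.6.3 requires an adverse event when a value is serious or leads to stopping study treatment. It otherwise exempts even clinically significant laboratory changes.
- Protocol 12.6.1.4 sets different criteria: symptoms, further testing or intervention, or study discontinuation or added therapy.
- Delay-level values need not stop treatment.
- The last dose is on Day 14, so values at Days 28, 42 and 56 have no remaining dose to stop. The sustained ALT/AST criterion, counted from the first scheduled post-baseline draw (Day 7, or Day 4 at the edge of the window), can be met only after Day 21 (or Day 18). A last dose within its window falls no later than Day 17.
- Under 12.6.3, collection ends 30 days after the last dose: 14 + 30 = Day 44, which is 12 days before the Day 56 laboratory visit. Protocol 6.4.2 instead has participants monitor events until the last study visit.

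**5. Visits.** The schedule of events, in both documents, has five post-baseline laboratory visits (Days 7, 14, 28, 42, 56). The laboratory text of SAP 7.8 names two (Days 7 and 56), although it also promises summaries at each scheduled visit. Followed literally, the list leaves Days 14, 28 and 42 out of the summaries.

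**6. Size of the listing task.** Six analytes carry limits: neutrophils, platelets, ALT, AST, total bilirubin and CPK. Assume that 2.5% of results fall beyond the relevant end of the reference range by chance. Then 6 × 5 visits × 36 × 0.025 = 27 flags, or 6 × 2 × 36 × 0.025 = 10.8 if only Days 7 and 56 count.

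**The case against.** A reader might infer that values meeting the protocol's limits disappear from the report altogether. The documents do not support that. The minimum and maximum are tabulated by arm, so a scheduled neutrophil count of 0.4 or platelet count of 45 is visible without any ULN. Values that stop treatment must be recorded as adverse events and so reach the event tables. An initial extreme value stays in the summary; only a value seen solely on a repeat or unscheduled draw is left out, and it is still listed. A reader might also picture a stopping-level value lost among flags for every analyte, both directions and all visits. On the relevant scope the number is about 27, and a listing shows the result beside its flag. So the counts could be made by hand: what is missing is a planned count, not the data. An independent committee also reviews accumulating safety data (protocol 7.7).

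Other fair points:
- The SAP takes precedence over the protocol in a discrepancy. Here, however, the protocol defers to the SAP, so there is no competing rule to override, only a task left undone.
- SAP Section 3 refers to mock tables that are not in the documents and might hold a definition. The protocol says that the SAP holds it.
- The lack of ULN conversion is read from the SAP's silence.
- The limits in 8.3.2 and 8.3.3 are examples tied to dosing, not a laboratory grading, and cover only six analytes. They are a minimum for the definition.
- The protocol promised a listing only. The by-arm count is an improvement on that promise, not part of it.

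**Conclusion.** The omission is confirmed on the face of the text: a definition and a listing are assigned to the SAP, are absent from it, and are not declared dropped. The consequence is narrower than lost data: no planned summary or dedicated listing identifies or counts the participants per arm who meet the protocol's own limits. This matters most for:
- ULN-based limits across about 15 centers;
- the joint ALT/AST and bilirubin criterion;
- delay-level values such as CPK;
- values seen only on repeat or unscheduled draws;
- values after Day 14, where adverse-event capture is uncertain.

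One missed participant is 1/12 = 8.3% of an arm. The conclusion about the text needs no numerical assumption. The ALT illustrations rest on the assumed ULNs and typical values given above, and the 27 flags on the assumed 2.5%. The change is worth making because it is cheap; the omission does not by itself invalidate the safety report.

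**What to change.** In SAP 7.8, for tabulation only and with no change to clinical management:

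1. Define markedly abnormal at least by the numeric limits already in protocol 8.3.2 and 8.3.3, state whether other analytes have a definition, and add the promised listing.
2. Tabulate by arm the number of participants meeting each limit after baseline, using scheduled, unscheduled and repeat values. Assess ALT/AST and bilirubin jointly, and the confirmed 5×ULN criterion with its stated duration. A single value above 5×ULN does not meet it.
3. Express ALT, AST, bilirubin and CPK as multiples of the local laboratory's ULN.
4. Reconcile the laboratory visit list with the schedule of events.

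Separately, protocol 6.4.2, 12.6.1.4 and 12.6.3 must be reconciled on when a laboratory finding is an adverse event and how long events are collected.

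The cost is SAP wording, one table, one listing that was already promised, and a little programming. The site reference ranges are already needed for the high/low flags.

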5.3. Clinical Development Program

In non-clinical safety pharmacology and toxicology studies, IRL201104 was safe and well tolerated at exposures up to 11 times higher than the highest dose level planned for the current Phase 2a clinical study. In 14-day rat and dog Good Laboratory Practice toxicology studies, the no-observed-effect-level was the highest dose tested (0.5 mg/kg intravenous [IV] bolus).

IRL201104 was assessed in a first-in-human (FIH) Phase 1 study in 62 healthy participants and participants with mild asthma in the United Kingdom (UK) (Study C1104-001). The highest dose tested was a single 8 mg dose (IV bolus) in 4 healthy participants and 6 participants with mild asthma. Most participants in the study received a single dose by IV bolus; however, 1 group (4 participants) received 3 single IV bolus injections of 2 mg (2 hours apart) on a single day. In this study, IRL201104 was well tolerated and safe, with no significant adverse events (AEs) reported for single doses up to 8 mg IRL201104. After a single 2, 4, and 8 mg IV bolus, IRL201104 was detectable in blood up to 15, 30, and 60 minutes, respectively, with exposure increasing in a dose-dependent manner. The mean $t_{1/2}$ of the 8 mg dose was approximately 16 minutes.

IRL201104 is currently being assessed for safety, tolerability, and PK in an ongoing Phase 1 multiple ascending dose (MAD) study in 18 healthy participants in the UK (Study C1104-003). The IRL201104 IV dose levels were 4 mg once daily (QD) for 5 days and 8 mg QD for 7 days. At each dose level, up to 8 participants received IRL201104 and 2 received placebo. Following a blinded review of safety data, study treatment was well tolerated in the groups receiving either IRL201104 4 mg (6 participants), 8 mg (8 participants) or placebo (4 participants) for 5 days and followed through Day 21.

In combination, these nonclinical data and a good clinical safety/tolerability profile show that IRL201104 is well suited for further development as a treatment for EoE.

This Phase 2a clinical study is a double-blind, placebo-controlled study designed to investigate the efficacy, safety, and tolerability of IRL201104 in adult participants with active EoE. Participants will receive a total of 3 doses of IRL201104 4 mg or 8 mg IV or placebo over a 14-day period. Study treatment will be delivered by IV bolus injection via cannula.

The justification for the dose levels selected in the current study is presented in Section [7.8](#).

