7.9. Schedule of Events

The visit schedule is presented in Table 3.

Table 3: Study RVL0 121-04 Schedule of Events

Procedures	Screening Period	Prior to Rand	Rand/ Baseline	Treatment Period				End of Study/ Final Safety	Notes
Visit	V-1	V0	V1	V2	V3	V4	V5	V6	
Week	-6	-	0	1	2	4	6	8	
Day	-	-	0	7	14	28	42	56	
Window	≤ 6 weeks	-	-	± 3 days	± 3 days	± 3 days	± 3 days	± 3 days	
Screening/ Baseline									
Informed consent	X	-	-	-	-	-	-	-	-
Demographics/ Medical history review	X	-	-	-	-	-	-	-	-
Inclusion/exclusion criteria review	X	X	X	-	-	-	-	-	
Treatment									
Randomization IWRs	-	-	X	-	-	-	-	-	
Administer study treatment	-	-	DBL	DBL	DBL	-	-	-	Pharmacy site staff will be unblinded to prepare the treatment. Investigators, study staff members, and study participants will be blinded to the treatment and dose level (4 mg or 8 mg or placebo) and will remain blinded throughout the study.
Efficacy	X	X	-	-	-	-	-	-	Daily completion of the DSQ starts on the first day it is issued to the participant.
DSQ training and issue handset	X	X	-	-	-	-	-	-	

Procedures	Screening Period	Prior to Rand	Rand/ Baseline	Treatment Period				End of Study/ Final Safety	Notes
Visit	V -1	V0	V1	V2	V3	V4	V5	V6	
Week	-6	-	0	1	2	4	6	8	
Day	-	-	0	7	14	28	42	56	
Window	≤ 6 weeks	-	-	± 3 days	± 3 days	± 3 days	± 3 days	± 3 days	
DSQ compliance assessment	-	-	X	X	X	X	X	X	
Retrieval of DSQ handset	-	-	-	-	-	-	-	X	
Esophageal endoscopy and biopsy with EoE-EREF5	EGD	-	-	-	-	X			-
EoEHSS - histology scoring	X	-	-	-	-	X			-
PGI-S	-	-	X	-	X	X	X	X	
PGI-C	-	-	-	-	X	X	X	X	
Safety									
Physical examination	X	-	X	X	X	X	X	X	Predose on Day 0.
ECG	X	-	X	X	X	X	X	X	
Height	X	-	-	-	-	-	-	-	
Weight	X	-	X	X	X	X	X	X	
Vitals	X	-	X	X	X	X	X	X	Should be measured within 15 minutes prior to dosing, and +15 minutes (+/- 5 minutes) postdose on Days 0, 7, and 14.
Diet history	X	X	X	X	X	X	X	X	
Concomitant medications and procedures	X	X	X	X	X	X	X	X	
Review of adverse events	-	X	X	X	X	X	X	X	

Procedures	Screening Period	Prior to Rand	Rand/ Baseline	Treatment Period				End of Study/ Final Safety	Notes
Visit	V -1	V0	V1	V2	V3	V4	V5	V6	
Week	-6	-	0	1	2	4	6	8	
Day	-	-	0	7	14	28	42	56	
Window	≤ 6 weeks	-	-	± 3 days	± 3 days	± 3 days	± 3 days	± 3 days	
Local laboratory									
Hematology and serum chemistry	X	-	X	X	X	X	X	X	
Coagulation	X	-	X	X	X	X	X	X	Should be performed before the procedure of endoscopy with esophageal biopsies on days the procedure is performed.
Urinalysis	X	-	X	X	X	X	X	X	
Serology	X	-	-	-	-	-	-	-	

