12.2. Vital Signs

Vital sign measurements include systolic and diastolic blood pressure, heart rate, temperature, and respiratory rate and will be assessed within 15 minutes predose and at 15 minutes (+/- 5 minutes) postdose.

Measurements should be made with participants in a sitting position, after resting for at least 5 minutes.

Height will be measured at screening only.

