2.2 Study Design

This is a Phase 2a, double-blind, placebo-controlled, multi-center study to assess the efficacy and safety of a repeat-dose regimen of IRL201104 in participants with active EoE. Eligible participants will undergo an up-to-6-week screening period to stabilize current therapy, confirm diagnosis by histologic assessment, and other eligibility criteria. Participant compliance to DSQ reporting will be assessed for at least 2 consecutive weeks prior to randomization. At the end of the screening period, eligible participants will be randomized in a 1:1:1 ratio to one of 3 arms, as displayed in Figure 1

- Arm 1: IRL201104 4 mg IV with endoscopy and esophageal biopsy 2 weeks after last dose (Week 4).
- Arm 2: IRL201104 8 mg IV with endoscopy and esophageal biopsy 2 weeks after last dose (Week 4).
- Arm 3: Placebo IV with endoscopy and esophageal biopsy 2 weeks after last dose (Week 4).

Participants will receive IRL201104 (4 mg or 8 mg IV) or placebo on Days 0, 7, and 14 (3 total doses over 14 days). Participants will be evaluated for clinical and histologic responses at Week 4. All participants will be assessed for safety and continued biomarker sampling through Week 8.

Figure 1: Overview on the Study Procedures

D = day; EGD = esophagogastroduodenoscopy; EOS = End of Study; ICF = informed consent form; IV = intravenous; R = randomization; WK = week

Table 1: Study Schema

The Schedule of Events for the study is

Procedures	Screening Period	Prior to Rand	Rand/ Baseline	Treatment Period				End of Study/ Final Safety	Notes
Visit	V -1	V0	V1	V2	V3	V4	V5	V6	
Week	-6	-	0	1	2	4	6	8	
Day	-	-	0	7	14	28	42	56	
Window	≤ 6 weeks	-	-	± 3 days	± 3 days	± 3 days	± 3 days	± 3 days	
Screening/ Baseline									
Informed consent	X	-	-	-	-	-	-	-	
Demographics/ Medical history review	X	-	-	-	-	-	-	-	
Inclusion/exclusion criteria review	X	X	X	-	-	-	-	-	
Treatment									
Randomization IWRS	-	-	X	-	-	-	-	-	
Administer study treatment	-	-	DBL	DBL	DBL	-	-	-	Pharmacy site staff will be unblinded to prepare the treatment. Investigators, study staff members, and study participants will be blinded to the treatment and dose level (4 mg or 8 mg or placebo) and will remain blinded throughout the study.
Efficacy									
DSQ training and issue handset	X	X	-	-	-	-	-	-	Daily completion of the DSQ starts on the first day it is issued to the participant.

Procedures	Screening Period	Prior to Rand	Rand/ Baseline	Treatment Period				End of Study/ Final Safety	Notes

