4 DEFINITIONS AND DERIVATIONS

Baseline: Baseline is defined as the last non-missing value (whether from scheduled or unscheduled visit) prior to the first study drug administration.

Change from Baseline: The change from baseline values at all post-baseline visits will be calculated by subtracting the baseline value from the corresponding post-baseline value.

Change from Baseline = Post baseline value - Baseline value.

Percent reduction: The percent reduction is the ratio of the reduction in the post-baseline value to its baseline value multiplied by 100.

$$\text{Percent reduction} = \frac{\text{Post Baseline value} - \text{Baseline value}}{\text{Baseline value}} \times 100$$

End of the Study: The end of the study is defined as the final follow-up visit by the last participant. If the study is terminated prematurely, the study ends when the sponsor notifies the investigator in writing that the study has finished, or when the last participant attends the final follow-up visit, whichever is later.

Study Day: This is the number of days from the date of the first study drug administration to a target date:

$$\begin{aligned} \text{Study Day} &= (\text{Target Date} - \text{Date of the first study drug administration}) + 1 \\ &\quad (\text{If target date is greater than or equal to the date of the first study drug administration}) \\ &\quad \text{or} \\ \text{Study Day} &= (\text{Target Date} - \text{Date of the first study drug administration}) \\ &\quad (\text{If target date is less than date of the first study drug administration.}) \end{aligned}$$

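### SAP 7.8 takes vital-sign change only from the baseline before the first dose, so no summary it defines gives the spread or extremes of the same-day post-dose change at doses 2 and 3

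*SAP*

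**What the plan says.** SAP 4 sets one baseline for all variables: "Baseline is defined as the last non-missing value (whether from scheduled or unscheduled visit) prior to the first study drug administration". It then defines change in the same way throughout: "The change from baseline values at all post-baseline visits will be calculated by subtracting the baseline value from the corresponding post-baseline value". SAP 7.8 applies this to blood pressure, heart rate, respiratory rate and temperature, which "will be summarized using the descriptive statistics for each vital sign measurement and change from baseline by treatment group, visit and timepoint". No reference value specific to each dose is defined. SAP 7.8 also plans a listing: "Vital Sign data will be listed by individual time course for each parameter".

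The timing of the readings is set in Protocol 7.9, Table 3 (repeated in the SAP 2.2 schedule): "Should be measured within 15 minutes prior to dosing, and +15 minutes (+/- 5 minutes) postdose on Days 0, 7, and 14". Protocol 12.2 agrees that vital signs "will be assessed within 15 minutes predose and at 15 minutes (+/- 5 minutes) postdose". Protocol 5.3 reports that the mean half-life "of the 8 mg dose was approximately 16 minutes".

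**The concern.** Each dosing day yields a pair of readings at most about 35 minutes apart (up to 15 minutes before the dose, up to 20 minutes after). The natural summary of such a pair is the post-dose value minus the pre-dose value of the same day. On Day 0 the SAP's rule gives that difference whenever the Day 0 pre-dose reading is present. On Days 7 and 14 it does not. The post-dose change is taken from a value one or two weeks old, and the reading made minutes earlier is summarized separately but not subtracted.

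Two of the three dosing days are affected, and they are the days on which a reaction after earlier exposure would show. Safety and tolerability are a secondary objective (Protocol 6.2). The adverse event tables are only a partial backstop. Protocol 12.6.3 says that clinically significant changes in blood pressure and pulse need not be reported as adverse events unless they are serious or lead to stopping treatment. Protocol 12.6.1.4 adds routes through symptoms, further testing, intervention or additional therapy. A transient fall without symptoms could therefore appear only in the vital-sign output. The out-of-range flags in SAP 7.8 apply to laboratory listings, and no threshold or outlier table for vital signs is described.

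**Working it through.** The documents give no SD, precision or power figure for vital signs, and the sample size is justified on clinical grounds only, so there is no stated figure to reproduce.

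**Inputs from the documents**
- Baseline and change: SAP 4.
- Doses on Days 0, 7 and 14: SAP 2.2.
- Reading times: Protocol 7.9 and 12.2.
- Half-life about 16 minutes at 8 mg: Protocol 5.3.
- About 36 participants randomized 1:1:1 (SAP 2.4), so 36/3 = 12 per arm.

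**Assumptions, not in the documents**
- The same SD, s, at every reading; s = 12 mmHg for systolic pressure as an illustration.
- Correlation 0.5-0.7 between readings on different days and 0.8-0.9 between the two readings of one visit.
- First-order elimination.

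**Step 1: what is subtracted.** Let B be the Day 0 pre-dose value, P the same-day pre-dose value and R the post-dose value. The planned change splits as

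R - B = (P - B) + (R - P).

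The first term is the shift between days, including any sustained effect. The second is the acute change. On Day 0, P = B and the two references coincide.

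**Step 2: is P a usable reference?** The fraction of drug left at 15 minutes is 0.5^(15/16) = 0.52 (0.65 at 10 minutes, 0.42 at 20 minutes), so the post-dose reading falls while drug is present. Seven days is 7 x 24 x 60 / 16 = 630 half-lives. With the 3-day windows, dose 2 could fall on Day 4 (360 half-lives after dose 1). If the windows apply independently, dose 3 could follow dose 2 by one day (Day 10 to Day 11), which is 24 x 60 / 16 = 90 half-lives. In every case drug carry-over into P is negligible. A sustained pharmacodynamic effect, which Protocol 7.8.2 infers from animal models, could still be present in P. For that the change from Day 0 remains the right measure.

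**Step 3: the mean.** When the same participants contribute both readings,

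mean(R - B) - mean(P - B) = mean(R - P),

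exactly. Both terms on the left are planned, so the mean acute change per arm can be recovered.

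**Step 4: the rest of the distribution.** Var(R - P) = Var(R) + Var(P) - 2 Cov(R, P), and no planned summary gives Cov(R, P). The median, minimum and maximum of R - P likewise cannot be obtained from the separate summaries of R and P. They need the individual pairs.

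**Step 5: spread.** For either reference, SD(change) = s x sqrt(2(1 - correlation)).

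| Reference | Correlation | SD of change | With s = 12 mmHg |
|---|---|---|---|
| Day 0 baseline | 0.5 | 1.00 s | 12.0 |
| Day 0 baseline | 0.6 | 0.89 s | 10.7 |
| Day 0 baseline | 0.7 | 0.77 s | 9.3 |
| Same-day pre-dose | 0.8 | 0.63 s | 7.6 |
| Same-day pre-dose | 0.85 | 0.55 s | 6.6 |
| Same-day pre-dose | 0.9 | 0.45 s | 5.4 |

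The smallest inflation is at 0.7 and 0.8: 0.775/0.632 = 1.22. At 0.6 and 0.85 it is 0.894/0.548 = 1.63. The largest is at 0.5 and 0.9: 1.00/0.447 = 2.24. If the two correlations are equal, the ratio is 1.

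**Step 6: one participant.** Take an invented systolic pressure of 120 before dose 1, 140 before dose 2 and 118 after dose 2. The planned change is 118 - 120 = -2. The acute change is 118 - 140 = -22. The table of observed values does not expose it either, because 118 is unremarkable taken alone. The example is built for contrast: a 20 mmHg rise between days is 20/12.0 = 1.7 to 20/9.3 = 2.2 SDs of the between-day change assumed above.

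**The case against.** The strongest reply is that nothing is lost. Observed values and changes are tabulated at each timepoint, the mean acute change follows from two planned means, and the listing puts each participant's pre-dose and post-dose values in time order. In the example above it would show 140 followed by 118. With about 12 participants per arm, and with SAP 3 resting all inference on clinical evaluation, that listing is a working part of the plan. Anaphylactic reactions, and acute allergic reactions needing immediate treatment, are events of special interest (Protocol 12.6.1.3) and are tabulated and listed under SAP 7.8. Protocol 15.3.3 asks only for vital signs at baseline and at each scheduled visit, so the SAP already goes further and breaks no commitment. Table layouts are left to mock outputs that are not in the documents reviewed.

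Most of this stands, and it rules out several stronger readings that a reader might infer:
- That the mean acute effect is biased or cannot be found. Step 3 shows otherwise for complete data, and the placebo arm is subject to day-to-day variation too.
- That a large individual fall would go unreported. It would be in the listing, though in no summary that the SAP text defines.
- That confidence intervals are needlessly wide. None is planned for safety data, so an argument about interval width does not apply.
- That the paired readings were scheduled specifically to detect acute reactions. The documents give their timing, not their purpose.

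What the reply does not answer is that the distribution of the acute change is in no defined summary. To obtain it, a reader must work out the differences for about 36 participants, five vital signs and two dosing days by hand.

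**Conclusion.** The point holds in a limited form. On Days 7 and 14 the only planned change score mixes day-to-day variation with the acute response, and the SD, median, minimum and maximum of the acute change are in no summary that the SAP text defines. The text alone settles this, with no assumption about variability; the one caveat is that the mock tables were not available.

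The size of the gain in spread is less certain. Inflation of about 1.2- to 2.2-fold rests wholly on the assumed correlations and disappears if readings a week apart are as closely correlated as readings within one visit. Even then, the same-day difference would remain the direct measure of the acute change. The recovery of the mean assumes complete pairs. SAP 3 imputes nothing, so with a missing reading the two planned means would cover different participants and the identity would be only approximate.

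The weight is minor to moderate: an optional improvement, not a defect that would mislead.

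**What to change.** In SAP 7.8, under Vital Signs, add one sentence: for Days 0, 7 and 14, the 15-minute post-dose value minus the same-day pre-dose value will be summarized for each vital sign by treatment group, with n (participants with both readings), mean, SD, median, minimum and maximum. Keep the change from the Day 0 baseline for the visit-to-visit summaries, where it describes sustained or cumulative shifts.

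The cost is that sentence and one table. It needs no new data or visits, adds no test and changes no clinical rule.
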